**\*\*\* Subject Population (h-m) \*\*\***

**8. Subject Population (Input N/A if not applicable)**

- h) **Inclusion and Exclusion Criteria (e.g., Participants must have 20/20 vision, Participants must be 30-45 years of age, etc.)**

**Identify inclusion criteria.**

We plan to recruit 120 men and women with an estimation that 15-25% of participants will not qualify (i.e., screen out) and 15-25% of participants will not complete the study (i.e. drop out). We plan to complete the study in 60 men and women aged >55 years who are prediabetic defined as impaired fasting glucose (100 to 126 mg/dl), HbA1c (5.7-6.4%), family history of type 2 diabetes, and/or impaired glucose tolerance defined as 2 hour postprandial blood glucose of 140 to 200 mg/dl. Participants will be eligible if they meet any 1 of these criteria.

10 healthy participants will be recruited who are 18-45 years old who have normal glucose values (fasting glucose <100mg/dl, HbA1c <5.7%, 2 hour postprandial blood glucose <140 mg/dl) and no family history of T2D.

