**3. Background**

**a) Describe past experimental and/or clinical findings leading to the formulation of the study, if applicable.**

Physical activity and the biguanide drug Metformin have been shown independently to reduce the incidence of T2D. Interestingly, these data also suggest in adults over the age of 60 metformin had marginal efficacy while physical activity lowered incidence of T2D by 70%. Currently, governing agencies recommend physical activity and metformin together for individuals with pre-diabetes of all ages to prevent the progression to overt T2D. Until recently, the interaction between exercise and metformin has been largely understudied. Members of our investigative team have previously showed that metformin does not enhance but may blunt the glucoregulatory and cardiovascular response to acute and chronic exercise, which is especially relevant to older adults. A purported mechanism of action is that metformin inhibits mitochondrial respiration, which likely limits VO2max and mitochondrial protein synthesis. We have previously demonstrated that post-aerobic exercise dairy feeding can improve VO2max to a greater extent than post-exercise carbohydrate beverage. Therefore, we feel dairy supplementation may override the potential inhibition of metformin on exercise adaptations and maximize the benefits for older adults. To date, real-time continuous glucose monitoring is limited in individuals at risk of T2D. Moreover, glucose profiles via CGM during or in response to exercise, metformin and/or post-exercise nutrition have yet to be fully characterized. Much clinical research is limited to measurements in the clinical research setting while real-time glucose monitoring performed in both the standardized clinical research setting and in free-living scenarios is novelty of the current study design that will close a gap in knowledge regarding glucoregulatory effects of exercise, metformin and/or standardized post-exercise nutrition.

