**\*\*\* Subject Population (a-g) \*\*\***

8. Subject Population - In the space below, please detail the participants that you are requesting to recruit (include requested participant number and description of each group requested). (Input N/A if not applicable)
- a) **Requested Participant Description (Include number of participants that you plan to study and description of each group requested, if applicable).**

We plan to recruit 120 men and women with an estimation that 15-25% of participants will not qualify (i.e., screen out) and 15-25% of participants will not complete the study (i.e. drop out). We plan to complete the study in 60 men and women aged >55 years who are prediabetic defined as impaired fasting glucose (100 to 126 mg/dl), HbA1c (5.7-6.4%), family history of type 2 diabetes, and/or impaired glucose tolerance defined as 2 hour postprandial blood glucose of 140 to 200 mg/dl. Participants will be eligible if they meet any 1 of these criteria.

10 healthy individuals, 18-45 years old who have normal glucose values (fasting glucose (<100mg/dl), HbA1c (<5.7%), 2 hour postprandial blood glucose (<140mg/dl)) or no family history of type 2 diabetes will be recruited.

Sub-study: 20 pre diabetic participants and 10 healthy individuals will complete the study.  
Subpopulation of [xx] participants will be recruited for Physical Activity Behavior Counseling (previously approved in Amendment 3.

- b) **What is the rationale for studying the requested group(s) of participants?**

Individuals at risk for T2D are the intended population for metformin; CGM; and Counseling studies. We will use a healthy control group to compare to individuals at risk for T2D.

- c) **If applicable, state the rationale for involvement of potentially vulnerable subjects to be entered into the study, including minors, pregnant women, economically and educationally disadvantaged, or decisionally impaired subjects. Specify the measures being taken to minimize the risks and the chance of harm to the potentially vulnerable subjects.**

We will not enroll minors, pregnant women, economically and educationally disadvantaged, or decisionally impaired subjects.

- d) **If women, minorities, or minors are not included, a clear compelling rationale must be provided. Examples for not including minors: disease does not occur in children; drug or device would interfere with normal growth and development; etc.**

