Minors are not included because the cost-benefit ratio is not clear and therefore inappropriate for this study.

- e) **State if any of the subjects are students, employees, or laboratory personnel. They should be presented with the same written informed consent. If compensation is allowed, they should also receive it.**

If any of the subjects are students, employees, or laboratory personnel they will be presented with the same written informed consent and compensation.

- f) **Describe how potential subjects will be identified for recruitment (e.g., chart review, referral from individual's treating physician, those individuals answering an ad). How will potential participants learn about the research and how will they be recruited (e.g., flyer, email, web posting, telephone, etc.)? Attach recruitment materials in the Attachment Section (#16). Important to remember: potential subjects may not be contacted before IRB approval.**

Potential subjects will be recruited initially from the Colorado State and Fort Collins community via email, electronic, newspaper, radio, or bulletin advertisements. Colorado State employees, local physicians and interested participants may be emailed for recruitment and communication purposes. Physicians will be contacted so if they have prediabetic patients they can be informed of the research study which includes standard care treatment options (i.e., physical activity and metformin). Text for advertisements will be obtained from the attached flyer. Information for local physicians is also attached.

- g) **If applicable, provide rationale for the inclusion of healthy volunteers in this study. Specify any risks to which these healthy volunteers may possibly be exposed. Specify the measures being taken to minimize the risks and the chance of harm to these volunteers.**

We will include healthy volunteers to compare to individuals at risk for T2D. No additional risks are known for healthy individuals compared to those at risk for T2D. Healthy individuals will not perform the intervention.

---

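### Family history of type 2 diabetes alone makes a participant prediabetic, so a pre-diabetes conclusion could cover people with normal glucose; the two definitions of the healthy group also conflict

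*Combined protocol and SAP*

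**What the plan says.** Sections 8a and 8h define the main-study population in the same way: over 55 and prediabetic by impaired fasting glucose, "HbA1c (5.7-6.4%), family history of type 2 diabetes, and/or impaired glucose tolerance". Both then state the combination rule: "Participants will be eligible if they meet any 1 of these criteria". The exclusion list in 8h removes diabetes but not normal glucose. The study overview in 2a screens out people who are not pre-diabetic, without giving another definition.

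The population is named in two ways. The title, the lay summary (1a) and the aims (1b) speak of older adults with pre-diabetes, and 1b treats them as diseased. Section 8b is broader: "Individuals at risk for T2D are the intended population for metformin; CGM; and Counseling studies". Section 8g agrees: "We will include healthy volunteers to compare to individuals at risk for T2D".

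The healthy group (18 to 45 years) is defined by normal glucose values, joined to family history differently in two places. Section 8a has "or no family history of type 2 diabetes will be recruited"; section 8h has "and no family history of T2D". This group is the comparator in the continuous glucose monitoring (CGM) sub-study: "Sub-study: 20 pre diabetic participants and 10 healthy individuals will complete the study".

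The Statistical Plan gives a Treatment Group by Time repeated-measures ANOVA and an unpaired t-test on change. It names no baseline covariate, no subset with measured dysglycaemia and no display of the qualifying criterion.

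**The concern.** Family history is a risk factor, not a glucose measurement. Someone who enters on it alone fits the at-risk label in 8b and 8g but not the pre-diabetes label in the title and aims. A result reported for pre-diabetes could then rest partly on people with normal glucose, in an unknown proportion, and a reader could not see how many.

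The healthy definition adds a second ambiguity. Read literally, the wording in 8a admits a volunteer with abnormal glucose and no affected relative, and one with normal glucose and an affected relative. The latter profile counts as prediabetic over 55. The CGM comparison meant to separate the two groups could then have that profile on both sides.

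**Working it through.** **Eligibility logic.** The rules in 8a and 8h, applied to the four combinations of glucose status and family history (age aside):

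| Glucose | Family history | Prediabetic (8a, 8h) | Healthy by 8a (or) | Healthy by 8h (and) |
|---|---|---|---|---|
| abnormal | no | yes | yes | no |
| abnormal | yes | yes | no | no |
| normal | no | no | yes | yes |
| normal | yes | yes | yes | no |

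The last row is the main point. The first and last rows show the two healthy definitions disagreeing on 2 of 4 profiles.

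**Illustration of dilution.** The documents give no power calculation, effect size, SD or family-history-only share, so there is no figure of the plan's to reproduce on this point. Assume a share p of 10%, 20% or 30%, 80% starting power, two-sided 0.05, equal groups and, at first, constant SD. Of 60 completers, p means 6, 12 or 18 people; of 20 prediabetic CGM participants, 2, 4 or 6. By the non-central t distribution, 80% power needs 0.736 SD at 30 v 30 and 1.060 SD at 15 v 15. The effect is multiplied by 1 − p if these participants have no response, and by 1 − p/2 if they have half. The powers are the same at both sizes.

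| Assumption for family-history-only participants | p = 10% | 20% | 30% |
|---|---|---|---|
| no effect, same SD | 71% | 61% | 50% |
| half effect, same SD | 76% | 71% | 66% |
| no effect, half the SD | 75% | 68% | 61% |
| half effect, half the SD | 79% | 78% | 77% |
| equal effect, same SD | 80% | 80% | 80% |

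The half-SD rows use a within-arm variance of 1 − 0.75p.

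**Precision of a dysglycaemic subset.** The 95% half-width for a difference in means, in SD units, is t(0.975, 2m − 2) × √(2/m), with m = n(1 − p) per group.

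| Full comparison | p = 0 | 10% | 20% | 30% |
|---|---|---|---|---|
| 30 v 30 | 0.52 | 0.55 | 0.58 | 0.62 |
| 15 v 15 | 0.75 | 0.79 | 0.85 | 0.91 |
| 10 v 10 | 0.94 | 1.00 | 1.07 | 1.16 |
| 5 v 5 | 1.46 | 1.58 | 1.73 | 1.94 |

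The first two rows are the main study with 60 completers, as two pooled halves and as two of four arms. The last two are CGM: 20 participants over four arms is 20/4 = 5 per arm if evenly spread, or 10 v 10 if arms are pooled in pairs.

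**Baseline adjustment (a separate matter).** The half-width of ANCOVA relative to the t-test on change is √[(1 − r²)(1 + 1/(N − 4)) / (2(1 − r))] × t(N − 3)/t(N − 2), where N is the total in the comparison and r an assumed pre-post correlation. For r = 0.5, 0.7 and 0.9 the ratio is 0.88, 0.94 and 0.99 at 15 v 15, but 0.96, 1.02 and 1.08 at 5 v 5.

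**The case against.** The strongest reply is that family history is a deliberate, pragmatic criterion, stated openly in two places, and that the trial may simply be studying people at risk. That is a fair reading of 8b and 8g, and nothing here argues against the criterion. It does not reconcile those sections with the title and aims.

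Further points on that side stand. The screening forms and GCP protocol among the attachments are not visible and might hold a stricter working definition. The or in 8a looks like a drafting slip, concerns 10 volunteers who receive no intervention, and feeds a comparison for which the Statistical Plan names no test. The mitochondrial and VO2max aims do not obviously depend on baseline glucose. That people with normal glucose have less room to improve is an assumption without support in the documents.

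Several stronger readings are tempting and should be resisted:

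- That people with normal glucose were enrolled. The documents show only that they could be.
- That the randomised comparison is biased. Every arm is drawn under the same rule, and 2a says subject characteristics are matched between groups, although it does not name them.
- That the qualifying criterion went unrecorded. The relevant forms cannot be seen.
- That one person could be in both groups. The age bands, over 55 and 18 to 45, do not overlap; only the profile can recur.
- That the background section also labels this sample as at risk. Its sentence "To date, real-time continuous glucose monitoring is limited in individuals at risk of T2D" describes earlier research, not this trial's participants.

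**Conclusion.** The point holds as one about labelling and generalisability, and should be acted on. On the visible text, family history alone is enough to be called prediabetic, no section requires an abnormal glucose or HbA1c value, and the population wording differs between the title and aims and sections 8b and 8g. The contradiction in the healthy definition is plain and affects the healthy-versus-prediabetic CGM comparison.

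The size is unknown. A reader might infer from the power table that the trial loses 10 to 30 percentage points of power. The documents do not support that: the share, starting power, effect and SD are all assumed, and the results run from no loss to a fall to 50%. Dilution of OGTT or CGM outcomes is a possibility only, and none is claimed for the mitochondrial or VO2max outcomes. The conclusion stands without those figures. Confidence is medium, because an unseen screening document could narrow the definition.

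**What to change.** 1. Reconcile the population wording across the title, 1a, 1b, 8a, 8b, 8g and 8h, and settle whether the healthy definition in 8a and 8h joins its parts by or or by and.
2. Either describe the whole sample as at risk for type 2 diabetes, or limit pre-diabetes conclusions to participants with measured dysglycaemia. In both cases show the qualifying criterion by arm.
3. Report glycaemic outcomes in participants with measured dysglycaemia beside the result in all analysed participants, as a sensitivity analysis. Use the plan's own ranges for fasting and 120-minute OGTT glucose, plus HbA1c if measured. The Statistical Plan is written in the past tense, so label this post hoc if outcomes have been seen. For CGM keep it descriptive: at about 5 per arm the half-width is already about 1.46 SD before any subsetting.

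The cost is wording, one table row and one extra analysis on OGTT samples already planned before and after training. No entry criterion changes. The downside is the wider intervals shown above. HbA1c is a criterion but is not named among the tests in 2a or 8i, although the blood panel list in 2a is open-ended. If it was not measured, participants who qualified only on HbA1c could not be placed, and precision would fall further.

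Separately, and not as a cure for the labelling: for OGTT outcomes in the main study, use ANCOVA on the post value adjusted for its own baseline. It should replace both the t-test on change and the Group by Time interaction, which for two groups and two time points is the same contrast. Label it post hoc if outcomes have been seen. It costs one degree of freedom. Do not extend it to CGM comparisons between arms, where at 5 v 5 it is no better from r = 0.7 upward.

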**Identify exclusion criteria.**

Medications contraindicated with Metformin (Dofetilide, Lamotrigine, Pegvisomant, Somatropin, Trimethoprim, Trospium, Gatifloxacin, Cephalexin, Cimetidine, Dalfampridine)  
Recent (less than 6 weeks) or planned imaging that requires IV contrast  
Renal failure, creatinine  $\geq$  1.3 mg/dL in men or  $\geq$  1.2 mg/dL in women  
ALT levels exceed 52 IU/L  
Heart, Kidney or Liver Disease  
Type I or Type II Diabetes  
Anti-coagulant therapy (warfarin/heparin)  
Lung/respiratory dysfunction  
Medications affecting primary outcomes  
Lactose Intolerant  
Tobacco Use  
Heavy Alcohol Use  
Cancer  
Lidocaine Allergy  
EKG that is nondiagnostic for ischemia, such as: Complete Left bundle branch block or nonspecific Intraventricular conduction delay with ST/T changes; LVH with significant ST changes; Wolff-Parkison-White syndrome; ventricular pacemaker; digoxin therapy with greater than 1 mm ST depression or  
Arrhythmias, such as: Uncontrolled rate in atrial fibrillation; nonsustained ventricular tachycardia.

- i) **Describe your screening procedures. Attach your screening document(s) (e.g., health history questionnaire) in the Attachment Section (#16).**

Blood draw for chemistry panel, health questionnaire, medical history questionnaire, oral glucose tolerance test, resting and exercise EC.

- j) **Describe how you will be cognizant of other protocols in which subjects might be participating. Please explain if subjects will be participating in more than one study.**

Subjects will be instructed to communicate with investigators should they consider or begin to participate in other studies. Subjects participating in studies that may confound the results of the present investigation will be asked to withdraw from the the present investigation.

- k) **Compensation. Explain the amount and schedule of compensation, if any, that will be paid for participation in the study. Compensation includes food, gift cards, money, tokens, etc. Include provisions for prorating payment, if applicable. Compensation should be prorated if several activities are involved for different time periods (e.g., \$10 for session #1, and \$10 for session #2).**

Pre diabetic objects will be paid \$500 at the completion of the study. Proration will occur at \$20 per oral glucose tolerance test and \$50 per muscle biopsy. Participants that complete the CGM portion of this study will receive additional compensation of \$100 because of the additional time required for this study component.  
Healthy participants will be compensated \$50 for the time spent completing the oral glucose tolerance test (OGTT) and up to 10 days of CGM.

- l) **Costs. Please explain any costs that will be charged to the subject.**

Subjects will not incur any costs.

- m) **Estimate the probable duration of the entire study. This estimate should include the total time each subject is to be involved and the duration the data about the subject is to be collected (e.g., This is a 2-year study. Participants will be interviewed 3 times per year; each interview will last approximately 2 hours. Total approximate time commitment for participants is 12 hours). These times should be consistent with the time commitment listed on the consent document.**

After initial screening Pre-diabetic subjects will undergo a 12 week intervention followed by post-intervention assessments. Total time demand for each subject is estimated at 15 weeks with a total

commitment of approximately 46 hours over that 15 weeks. If participants chose to participate in the optional physical activity behavior counseling there will be additional time spent completing questionnaires (less than 1 hr) at baseline, immediately after completion of exercise training and 12 weeks after completion of exercise training but these can be completed via email or phone. Additionally, participants will be randomized to complete 1 session of in person physical activity behavior counseling (approximately 1 hour).

Pre-diabetic subjects who choose to participant in wearing the Dexcom G6 CGM will wear it for up to 10 days at a time on three separate occasions: before, during and after the 12-week intervention.

Healthy subjects who participant in wearing the Dexcom G6 CGM will wear it for up to 10 days on one occasion.

-----  
**\*\*\* Risks \*\*\***

**9. Risks (Input N/A if not applicable)**

US Department of Health & Human Services (HHS) Regulations define a subject at risk as follows: "...any individual who may be exposed to the possibility of injury, including physical, psychological, or social injury, as a consequence of participation as a subject in any research, development, or related activity which departs from the application of those accepted methods necessary to meet his needs, or which increases the ordinary risks of daily life, including the recognized risks inherent in a chosen occupation or field of service."

a) **PI's evaluation of the overall level of Risk. (Please check one: minimal or > minimal.)**

**Minimal (everyday living)**

**Y > Minimal (greater than everyday living)**

b)

For the following categories include a scientific estimate of the frequency, severity, and reversibility of potential risks. Wherever possible, include statistical incidence of complications and the mortality rate of proposed procedures. Where there has been insufficient time to accumulate significant data ON risk, a statement to this effect should be included. (In describing these risks in the consent form to the subject, it is helpful to use comparisons which are meaningful to persons unfamiliar with medical terminology.) Address any risks related to:

**1. Use of investigational devices. Please include the clinical adverse events (AEs) associated with each of the devices with an indication of frequency, severity and reversibility. This information can often be found in the Investigator(s) brochure.**

Dexcom CGM G6 is not an FDA approved device. This is currently available for research and investigational purposes. Please see IB in attachments and notes in protocol notes. Wearing of device should not be placed through baggage x-ray machine or body scanner. Rarely, the sensor wire may break or detach from the sensor pod. These do not pose a significant medical risk, but participants should contact the Study Coordinator within 24 hours if experiencing a broken wire. Risks include infection, bleeding, pain or skin irritations (e.g., redness, swelling, bruising, itching, scarring or skin discoloration) from the sensor and wearing the adhesive patch.

**2 Use of investigational drugs. Please include the clinical AEs associated with each of the drugs with an indication of frequency, severity and reversibility. This information can often be found in the Investigator(s) brochure.**

n/a

**3 Use of commercially available drugs, reagents or chemicals. Please include the clinical AEs associated with each of the drugs with an indication of frequency, severity and reversibility. This information can often be found in the package insert provided by the manufacturer.**

Metformin has been commonly used as a diabetes medication for many years, both within and outside of the US. It is safely used by nearly 50 Million people on a daily basis in the US. Like most medication there are possible side effects: From the MAYO CLINIC:

Risks:

More common

Abdominal or stomach discomfort  
Cough or hoarseness  
Decreased appetite  
Diarrhea  
Fast or shallow breathing  
Fever or chills  
General feeling of discomfort  
Lower back or side pain  
Muscle pain or cramping  
Painful or difficult urination  
Sleepiness

Less common

Anxiety  
Blurred vision  
Chest discomfort  
Cold sweats  
Coma  
Confusion  
Cool, pale skin  
Depression  
Difficult or labored breathing  
Dizziness  
Fast, irregular, pounding, or racing heartbeat or pulse  
Feeling of warmth  
Headache  
Increased hunger  
Increased sweating  
Nausea  
Nervousness  
Nightmares  
Redness of the face, neck, arms, and occasionally, upper chest  
Seizures  
Shakiness  
Shortness of breath  
Slurred speech  
Tightness in the chest  
Unusual tiredness or weakness  
Wheezing

Rare

Behavior change similar to being drunk  
Difficulty with concentrating  
Drowsiness  
Lack or loss of strength  
Restless sleep  
Unusual sleepiness

**4 When performing procedures, please include all investigational, non-investigational and non-invasive procedures (e.g., surgery, blood draws, treadmill tests).**

Catheter Placement for OGTT (beginning and end of study): Minor discomfort of having the

needle inserted and taped to an arm. In about 1 in 10 cases, a small amount of bleeding will occur under the skin that will cause a bruise. The risk of forming a blood clot in the vein is about 1 in 100, and the risk of significant blood loss is 1 in 1,000. This procedure is currently CSU-IRB approved and active.

Muscle biopsy (beginning and end of study): The risk of allergic reaction to lidocaine and lidocaine toxicity is extremely low (0 in the ~1500 cases witnessed by PI). There is a small risk of infection at the site of incision. There is a small risk of the incision reopening/bleeding after the subject leaves the lab. All subjects will have a small scar at the incision site. The rate and degree of healing varies considerably, but it is expected that scars will be difficult to see within 6-12 months after the procedure.

Consumption of Heavy Water: Brief periods (< 30 minutes) of dizziness have been reported in a small number of people (< 5%) after drinking special water. This is due to the special water being heavier than normal water. Heavier water can temporarily disrupt your inner ear ability to control balance, producing a sensation of dizziness.

Exercise and Exercise Testing (VO2max): There is a very small chance of an irregular heartbeat during exercise (< 1% of all subjects). Other rare risks of a stress test are heart attack (< 5 in 10,000) and death (<2 in 10,000). Wearing a mouthpiece and nose-clip during the graded exercise test can sometimes cause dryness in the mouth and mild discomfort.

CGM: The insertion of the CGM is a very quick procedure that causes no more discomfort than the blood sampling or finger prick. The sensor sits beneath the skin and the participant should not feel the sensor once it is inserted. There is a small risk of infection, bleeding, pain or skin irritations (e.g., redness, swelling, bruising, itching, scarring or skin discoloration) after inserting the CGM sensor and wearing the adhesive patch. To minimize the risk of discomfort, researchers will clean the area of skin with sterile alcohol swabs. The sensors and applicator are shipped in sterile packaging and will be inserted within 5 minutes of opening package. Over 325 G6 CMG devices have been studied in 241 subjects across 9 independent clinical study sessions. There were 5 total adverse events reported in these studies that included reddening, irritation, infection and shooting pain at the site of the insertion or adhesive site that resolved within 24 hours. No serious adverse device effects or unanticipated adverse device effects were reported. A detailed report can be found in the investigational brochure in Section 4 Existing Clinical Data.

Fingersticks: Participants will likely experience brief (<30s) physical discomfort during the finger stick procedure when the lancet goes into your finger. In about 10% of the cases a small amount of bleeding under the skin will produce a bruise. A small scare may persist for several weeks. The risk of local infection is less than 1 in 1,000 and is minimized by using the alcohol (70% ethanol) swabs provided.

